3.3 SELECTION OF TRIAL POPULATION

It is planned that 15 healthy male and female subjects (if feasible at least 5 of each sex) will enter the study. They will be recruited from the volunteers' pool of the trial site.

A log of all subjects enrolled into the trial (i.e. who have signed informed consent) will be maintained in the ISF irrespective of whether they have been treated with investigational drug or not.

3.3.1 Main diagnosis for trial entry

The study will be performed in healthy subjects.

3.3.2 Inclusion criteria

Subjects will only be included in the trial if they meet the following criteria:

1. Healthy subjects according to the assessment of the investigator, as based on a complete medical history including a physical examination, vital signs (BP, PR), 12-lead ECG, and clinical laboratory tests
2. Age of 18 to 55 years (inclusive)
3. BMI of 18.5 to 29.9 kg/m² (inclusive)
4. Signed and dated written informed consent prior to admission to the study, in accordance with GCP and local legislation
5. Male subjects, or female subjects who meet any of the following criteria from at least 30 days before the first administration of trial medication until 30 days after trial completion:
 - Use of adequate contraception, e.g. any of the following methods *plus* condom: implants, injectables, combined oral or vaginal contraceptives, intrauterine device
 - Sexually abstinent
 - A vasectomised sexual partner (vasectomy at least 1 year prior to enrolment)
 - Surgically sterilised (including hysterectomy or bilateral tubal occlusion)
 - Postmenopausal, defined as at least 1 year of spontaneous amenorrhea (in questionable cases a blood sample with levels of FSH above 40 U/L and estradiol below 30 ng/L is confirmatory)

3.3.3 Exclusion criteria

Subjects will not be allowed to participate, if any of the following general criteria apply:

1. Any finding in the medical examination (including BP, PR or ECG) deviating from normal and assessed as clinically relevant by the investigator
2. Repeated measurement of systolic blood pressure outside the range of 90 to 140 mmHg, diastolic blood pressure outside the range of 50 to 90 mmHg, or pulse rate outside the range of 45 to 90 bpm

3. Any laboratory value outside the reference range that the investigator considers to be of clinical relevance
4. Any evidence of a concomitant disease assessed as clinically relevant by the investigator
5. Gastrointestinal, hepatic, renal, respiratory, cardiovascular, metabolic, immunological or hormonal disorders
6. Cholecystectomy or other surgery of the gastrointestinal tract that could interfere with the pharmacokinetics of the trial medication (except appendectomy or simple hernia repair)
7. Diseases of the central nervous system (including but not limited to any kind of seizures or stroke), and other relevant neurological or psychiatric disorders
8. History of relevant orthostatic hypotension, fainting spells, or blackouts
9. Chronic or relevant acute infections
10. History of relevant allergy or hypersensitivity (including allergy to the trial medication or its excipients)
11. Use of drugs within 30 days of planned administration of trial medication that might reasonably influence the results of the trial (including drugs that cause QT/QTc interval prolongation)
12. Intake of an investigational drug in another clinical trial within 60 days of planned administration of investigational drug in the current trial, or concurrent participation in another clinical trial in which investigational drug is administered
13. Smoker (more than 10 cigarettes or 3 cigars or 3 pipes per day)
14. Inability to refrain from smoking on specified trial days
15. Alcohol abuse (intake of more than 20 g per day for females and 30 g per day for males)
16. Drug abuse or positive drug screening
17. Blood donation of more than 100 mL within 30 days of planned administration of trial medication or intended blood donation during the trial
18. Intention to perform excessive physical activities within one week prior to the administration of trial medication or during the trial
19. Inability to comply with the dietary regimen of the trial site
20. A marked baseline prolongation of QT/QTc interval (such as QTc intervals that are repeatedly greater than 450 ms in males or repeatedly greater than 470 ms in females) or any other relevant ECG finding at screening
21. A history of additional risk factors for *Torsade de Pointes* (such as heart failure, hypokalaemia, or family history of Long QT Syndrome)
22. Subject is assessed as unsuitable for inclusion by the investigator, for instance, because the subject is not considered able to understand and comply with study requirements, or has a condition that would not allow safe participation in the study
23. Male subjects with WOCBP partner who are unwilling to use male contraception (condom or sexual abstinence) from time point of first administration of trial medication until 30 days after the last administration of trial medication
24. For female subjects, positive pregnancy test, pregnancy, or plans to become pregnant within 30 days after study completion

25. For female subjects, lactation period
26. During COVID-19 pandemic: laboratory test indicative of an ongoing SARS-CoV-2 infection
27. Hypokalemia, hypomagnesemia, or hypercalcemia
28. PQ interval greater than 220 ms in the ECG at screening
29. Marked conductivity disorders (e.g. sinu-atrial blocks of II° or III°) or sick sinus syndrome, thoracic aneurysm of the aorta
30. Known or suspicion of pre-excitation syndrome (WPW- or LGL syndrome)
31. Known myopathy, personal or family history of hereditary muscular disorders, or history of muscular toxicity with another statin or fibrate; Asian ancestry; hypothyroidism
32. Hereditary fructose intolerance, lactose intolerance, glucose-galactose malabsorption, sucrose-isomaltase deficiency
33. History of nephrolithiasis
34. Gout or clinically relevant elevation of uric acid
35. Clinically relevant hypoproteinemia at screening
36. TSH exceeds upper limit of norm at screening, confirmed by a repeat test
37. Creatinine clearance (according to CKD EPI formula) is lower than 80 ml/min confirmed by a repeat test
38. Subjects with any other condition that would preclude administration of digoxin, furosemide, metformin or rosuvastatin (i.e. contraindicated as per SmPC), such as hypersensitivity to active ingredient or any of the excipients or to sulphonamides, active liver disease including elevations of serum transaminases exceeding 2 times the upper limit of normal upon repeat test, hypovolaemia or dehydration, partial obstructions of urinary outflow (e.g. prostatic hypertrophy)

For study restrictions, refer to Section [4.2.2](#).

3.3.4 Withdrawal of subjects from treatment or assessments

Subjects may discontinue trial treatment or withdraw consent to trial participation as a whole ('withdrawal of consent') with very different implications; please see Sections [3.3.4.1](#) and [3.3.4.2](#) below.

If a subject is removed from or withdraws from the trial prior to the first administration of trial medication, the data of this subject will not be entered in the case report form (CRF) and will not be reported in the clinical trial report (CTR). If a subject is removed from or withdraws from the trial after the first administration of trial medication, this will be documented and the reason for discontinuation must be recorded in the CRF; in addition, the data will be included in the CRF and will be reported in the CTR. At the time of discontinuation, a complete end of trial examination will be performed, if possible, and the information will be recorded in the CRF. If the discontinuation occurs before the end of the REP (see Section [1.2.3](#)), the discontinued subject should if possible be questioned for AEs and concomitant therapies at or after the end of the REP in order to ensure collection of AEs

and concomitant therapies throughout the REP, if not contrary to any consent withdrawal of the subject.

If it is known that a subject becomes pregnant during the trial, administration of the trial medication is to be stopped immediately, and the subject is to be removed from the trial. The subject is to be followed until she has given birth or until the end of the pregnancy. The subject's data are to be collected until the end of the trial (last visit of last subject) and reported in the CTR. For reporting of pregnancy and associated events, refer to Section [5.2.5.2.4](#).

3.3.4.1 Discontinuation of trial treatment

An individual subject will discontinue trial treatment if:

1. The subject wants to discontinue trial treatment, without the need to justify the decision
2. The subject has repeatedly shown to be non-compliant with important trial procedures and, in the opinion of both, the investigator and sponsor representative, is not willing or able to adhere to the trial requirements in the future.
3. The subject needs to take concomitant medication that interferes with the investigational medicinal product or other trial treatment
4. The subject can no longer receive trial treatment for medical reasons (such as pregnancy, surgery, adverse events [AEs], or diseases)
5. The subject has an elevation of AST and/or ALT ≥ 3 -fold ULN and an elevation of total bilirubin ≥ 2 -fold ULN (measured in the same blood sample) and/or needs to be followed up according to the DILI checklist provided in the ISF
6. In addition to these criteria, the investigator may discontinue subjects at any time based on his or her clinical judgment.

Even if the trial treatment is discontinued, the subject remains in the trial and, given his/her agreement, will undergo the procedures for early treatment discontinuation and follow up as outlined in the [Flow Chart](#) and Section [6.2.3](#).

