5.2.3 Safety laboratory parameters

For the assessment of laboratory parameters, blood and urine samples will be collected by the trial site at the times indicated in the Flow Chart after the subjects have fasted for at least 10 h with the exception of safety lab B which may be taken under non-fasted conditions. For retests, at the discretion of the investigator or designee, overnight fasting is not required.

The parameters that will be determined are listed in Tables [5.2.3: 1](#) and [5.2.3: 2](#). Reference ranges will be provided in the ISF, Section 10.

Manual differential white blood cell count or urine sediment examinations will only be performed if there is an abnormality in the automatic blood cell count or in the urinalysis, respectively. Blood sampling for lymphocyte differentiation may be separated from the rest of safety lab B, should safety lab B fall on a Sunday. In these cases blood for lymphocyte differentiation will be withdrawn in an additional blood sample on Sunday evenings to ensure sufficient stability of samples until measurement the next day. This is acceptable since it is only a logistical step which ensures sample stability but does not influence the timepoint of availability of these safety data, i.e. only on the Monday either way, and has no impact on subjects' safety.

Table 5.2.3: 1 Routine laboratory tests

Functional lab group	BI test name [comment/abbreviation]	A ¹	B ¹	C ¹
Haematology	Haematocrit	X	X	X
	Haemoglobin	X	X	X
	Red Blood Cell Count/Erythrocytes	X	X	X
	White Blood Cells/Leucocytes	X	X	X
	Platelet Count/Thrombocytes (quant)	X	X	X
Automatic WBC differential, relative	Neutrophils/Leukocytes; Eosinophils/Leukocytes; Basophils/Leukocytes; Monocytes/Leukocytes; Lymphocytes/Leukocytes	X	-	X
Automatic WBC differential, absolute	Neutrophil, absol.; Eosinophils, absol.; Basophils, absol.; Monocytes, absol.; Lymphocytes, absol.	X	-	X
Manual differential WBC (if automatic differential WBC is abnormal)	Neut. Poly (segs); Neut. Poly (segs), absol.; Neutrophils Bands; Neutrophils Bands, absol.; Eosinophils/Leukocytes; Eosinophils, absol.; Basophils/Leukocytes; Basophils, absol.; Monocytes/Leukocytes; Monocytes, absol.; Lymphocytes/Leukocytes; Lymphocytes, absol.			
Lymphocyte differentiation (relative and absolute; except for ratio)	T cells (CD3+), T helper cells (CD3+CD4+), cytotoxic T cells (CD3+CD8+), B cells (CD19+), natural killer cells (CD16+CD56+CD3-), double-positive T cells (CD3+CD4+CD8+), CD4:CD8 ratio	X	X	X

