Coagulation	Activated Partial Thromboplastin Time	X	-	X
	Prothrombin time - INR (International Normalization Ratio)	X	-	X
Enzymes	AST [Aspartate transaminase] /GOT	X	X	X
	ALT [Alanine transaminase] /GPT	X	X	X
	Alkaline Phosphatase	X	X	X
	Gamma-Glutamyl Transferase	X	X	X
	Creatine Kinase [CK]	X	X	X
	Creatine Kinase Isoenzyme MB [only if CK is elevated]	-	-	-
Hormones	Thyroid Stimulating Hormone	X	-	-
Substrates	Glucose (Plasma)	X	-	-
	Creatinine	X	X	X
	GFR/ CKD-EPI ³	X	-	-
	Bilirubin, Total	X	-	X
	Bilirubin, Direct	X	-	X
	Protein, Total	X	-	X
	C-Reactive Protein (Quant)	X	X	X
	Uric Acid	X	-	-
Electrolytes	Sodium	X	X	X
	Potassium	X	X	X
	Calcium	X	X	X
	Magnesium	X	X	X
	Chloride	X	X	X

Cont'd Table 5.2.3: 1 Routine laboratory tests

Urinalysis ² (Stix)	Urine Nitrite (qual)	X	-	-
	Urine Protein (qual)	X	-	-
	Urine Glucose (qual)	X	-	-
	Urine Ketone (qual)	X	-	-
	Urobilinogen (qual)	X	-	-
	Urine Bilirubin (qual)	X	-	-
	Urine RBC/Erythrocytes (qual)	X	-	-
	Urine WBC/Leucocytes (qual)	X	-	-
	Urine pH	X	-	-
Urine sediment ²	Only positive findings will be reported (for instance, the presence of sediment bacteria, casts in sediment, squamous epithelial cells, erythrocytes, leukocytes)			

- 1 A to be done at screening examination, B during the trial, C at EoTrial examination.
- 2 Microscopic examination if erythrocytes, leukocytes, or protein are abnormal in urine
- 3 Estimated glomerular filtration rate according to CKD-EPI formula [R12-1392]

The tests listed in Table [5.2.3: 2](#) are exclusionary laboratory tests that may be repeated as required. The results will not be entered in the CRF/database and will not be reported in the CTR. Except for pregnancy tests and drug screening, it is planned to perform these tests during screening only. Pregnancy testing in women will be performed at screening, upon admission in the evening of Day -1 of both treatment periods, prior to the first administration of BI 730357, and as part of the end of trial examination. Drug screening will be performed at screening and upon admission in the evening of Day -1 of both treatment periods.

Table 5.2.3: 2 Exclusionary laboratory tests

Functional lab group	Test name
Drug screening (urine)	Amphetamine/MDA
	Barbiturates
	Benzodiazepine
	Cannabis
	Cocaine
	Methadone
	Methamphetamines/MDMA/XTC
	Opiates
	Phencyclidine
	Tricyclic antidepressants
Infectious serology (blood)	Hepatitis B surface antigen (qualitative)
	Hepatitis B core antibody (qualitative)

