5.2.5.1.4 Adverse events of special interest

The term adverse events of special interest (AESI) relates to any specific AE that has been identified at the project level as being of particular concern for prospective safety monitoring and safety assessment within this trial, e.g. the potential for AEs based on knowledge from other compounds in the same class. AESIs need to be reported to the sponsor’s Pharmacovigilance Department within the same timeframe that applies to SAEs, please see Section [5.2.5.2.2](#).

The following are considered as AESIs:

- Hepatic injury
A hepatic injury is defined by the following alterations of hepatic laboratory parameters:
 - o An elevation of AST (aspartate transaminase) and/or ALT (alanine transaminase) ≥ 3 -fold ULN combined with an elevation of total bilirubin ≥ 2 -fold ULN measured in the same blood sample, or
 - o Aminotransferase (ALT, and/or AST) elevations ≥ 10 fold ULN

These lab findings constitute a hepatic injury alert and the subjects showing these lab abnormalities need to be followed up according to the 'DILI checklist' provided in the ISF. In case of clinical symptoms of hepatic injury (icterus, unexplained encephalopathy, unexplained coagulopathy, right upper quadrant abdominal pain, etc.) without lab results (ALT, AST, total bilirubin) available, the Investigator should make sure that these parameters are analyzed, if necessary in an unscheduled blood test. Should the results meet the criteria of hepatic injury alert, the procedures described in the DILI checklist should be followed.

- Severe infections (grading according to Rheumatology Common Toxicity Criteria [RCTC] developed by OMERACT [[R13-3515](#)])
- Opportunistic and mycobacterium tuberculosis infections

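### The on-trial safety panel measures AST and ALT but not total bilirubin, so the combined hepatic stopping criterion cannot be evaluated from any scheduled sample during dosing

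*Protocol*

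**What the plan says.** **Stopping rule.** Protocol Section 3.3.4.1, item 5, makes discontinuation mandatory when AST and/or ALT is at least 3-fold ULN and total bilirubin at least 2-fold ULN, with the two "measured in the same blood sample) and/or needs to be followed up according to the DILI checklist provided in the ISF".

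**AESI.** Section 5.2.5.1.4 defines hepatic injury by either of two limbs. One is AST/ALT of at least 3-fold ULN "combined with an elevation of total bilirubin" of at least 2-fold ULN in the same sample. The other, "Aminotransferase (ALT, and/or AST) elevations" of at least 10-fold ULN, needs no bilirubin.

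**Laboratory sets.** Table 5.2.3: 1 has columns A, B and C. The ALT row reads "ALT [Alanine transaminase] /GPT X X X", and AST is marked the same way. The bilirubin row reads "Bilirubin, Total X - X". Footnote 1 assigns the sets: "A to be done at screening examination, B during the trial, C at EoTrial examination".

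**Provisions for extra tests.** Section 5.2.5.1.4 tells the investigator to obtain missing liver parameters, but the instruction opens "In case of clinical symptoms of hepatic injury". Section 5.2.3 leaves repeat testing to judgement: "For retests, at the discretion of the investigator or designee, overnight fasting is not required". Section 6.2.3 requires follow-up testing of abnormal values that the investigator judges clinically relevant.

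**The concern.** A mandatory stopping criterion needs two analytes from one sample, and the panel scheduled during dosing supplies only one of them. In an asymptomatic subject whose ALT rises to, say, 5-fold ULN, the scheduled sample cannot show whether the rule has been met. No visible text requires bilirubin to be added. Protocol Section 1.4.2.4 says the trial requires timely detection of liver laboratory changes, and for this limb the schedule does not provide it.

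The liver question is relevant here. Section 1.2.2 notes dose-dependent transaminase rises with rosuvastatin. Section 1.4.2.3 says the risk from raised rosuvastatin exposure, if OATPs and BCRP are both inhibited, cannot be assessed.

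There is also a reporting effect. The hepatic AESI count rests on investigator classification (SAP Section 7.8.1) and may be incomplete for the combined limb. SAP Section 7.8.2 plans a table of shifts from baseline to the last value on treatment, and for total bilirubin in completers that table has no scheduled on-treatment value.

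**Working it through.** The plan states no figure to reproduce. The check sets the laboratory columns of Table 5.2.3: 1 against the safety-laboratory marks in the two flow charts.

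**Scheduled blood panels between first cocktail dose and end of trial.** Times are hours relative to cocktail dosing in that period. The other marks in the column are urine drug screen, breath alcohol and pregnancy tests.

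| Period | Time | Set | AST/ALT | Total bilirubin | BI 730357 doses already given |
|---|---|---|---|---|---|
| 1 | 24 h | B | yes | no | 0 (cocktail only) |
| 2 | −170 h | B | yes | no | 0 (same slot as first dose) |
| 2 | −74 h | B | yes | no | 8 |
| 2 | 24 h | B | yes | no | 17 |
| 2 | 95 h | B | yes | no | 23 |

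Panels with AST/ALT: 5 of 5. Panels with total bilirubin: 0 of 5. Panels on which the combined limb can be evaluated: 0 of 5.

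**Dose counts.** Planned doses are 13 days × 2 = 26.
- Before −74 h: Days −7 to −4, 4 × 2 = 8 (the dose in the −74 h slot itself is not counted).
- By 24 h: 8 plus the doses at −74, −62, −50, −38, −26, −13, −1, 11 and 23 h = 8 + 9 = 17.
- By 95 h: 17 plus the doses at 35, 47, 58.5, 70.5, 82.5 and 94.5 h = 17 + 6 = 23.
- Remaining: 106.5, 118.5 and 130.5 h = 3, and 23 + 3 = 26.

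**Samples.** All set B draws: 5 × 15 = 75. Draws clearly under BI 730357 dosing (−74, 24 and 95 h): 3 × 15 = 45.

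**Next scheduled bilirubin for completers.** Set C is taken on Day 14–22 and the last dose is on Day 6. The gap is 14 − 6 = 8 to 22 − 6 = 16 days.

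**On-treatment window.** SAP Table 6.1: 1 ends the last on-treatment phase 7 × 24 h after the last BI 730357 dose, unless trial termination comes first. 130.5 + 168 = 298.5 h after cocktail dosing on Day 1 at 09:00, which is Day 13 at 19:30. The earliest end-of-trial examination is Day 14, so a completer's set C value falls in follow-up.

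**Range left uncovered.** At 10-fold ULN or above, set B alone meets the AESI definition, and the DILI-checklist clause of item 5 applies. With clinical symptoms, bilirubin must be obtained. What remains is AST/ALT from 3-fold to below 10-fold ULN with bilirubin at least 2-fold ULN and no symptoms.

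**The case against.** The strongest reply is that the criterion is delayed, not disabled. Neither section says the qualifying sample must be a scheduled one, so a single unscheduled retest measuring both analytes would satisfy it. The trigger is visible at every draw. Transaminases above 2-fold ULN on repeat are exclusionary, so a new 3-fold value would stand out. An investigator who judges it relevant must follow it with appropriate tests, and may stop dosing under item 4 or 6. The uncovered range is narrow, and nothing in the documents estimates how often it would arise in 15 healthy subjects over 13 days. Set B also omits coagulation, direct bilirubin, total protein and the white-cell differential, which suggests deliberate tiering. The DILI checklist is held in the investigator site file and may say more.

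Much of this stands, and it limits the consequence. It does not close the gap, because each route depends on the investigator's judgement while the stopping rule is mandatory. Section 5.2.5.1.4 invokes the checklist for subjects who already show alert findings, so on the visible text it does not supply the bilirubin needed to recognise an alert. Early discontinuers have set C at the end-of-trial examination, if possible, but only after the decision to stop. The end-of-trial bilirubin remains available for descriptive summaries over time, so the SAP effect is confined to on-treatment displays.

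**Conclusion.** The concern holds. As scheduled, the combined limb of the hepatic stopping rule and of the hepatic AESI cannot be evaluated on any of the five panels between first dose and end of trial, three of which fall clearly under BI 730357 dosing. The exposed range is an asymptomatic rise of AST/ALT from 3-fold to below 10-fold ULN. The limb at 10-fold or above is unaffected, as are all primary and secondary endpoints.

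The sample counts measure assays not planned, not events missed; the probability of a missed event cannot be derived from the documents and is likely small at this sample size. The conclusion assumes 15 subjects who complete as scheduled. It rests on the visible text, and the DILI checklist could not be checked. The point should be fixed because it leaves a mandatory safety rule dependent on an optional test and the remedy is cheap.

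**What to change.** Preferred: mark total bilirubin in column B of Table 5.2.3: 1. This is one table cell by amendment and adds at most 75 assays (15 subjects × 5 draws) on blood already being drawn, with no extra visit or venepuncture. The combined limb then becomes evaluable on 5 of 5 panels, and the SAP shift table gains on-treatment bilirubin values.

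Alternative: add one sentence to Sections 5.2.3 and 5.2.5.1.4 requiring total bilirubin from the same sample whenever AST or ALT is at least 3-fold ULN. The table already has a reflex test of this kind, CK-MB when CK is raised. It costs fewer assays but depends on usable residual sample, on which the documents are silent. The sentence should therefore call for a prompt repeat draw measuring both analytes when none remains. It would also leave the SAP shift table without routine on-treatment bilirubin.

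The stopping criterion and the AESI definition stay as written under either option.
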